3.1 Study Design

3.1.1 Description

This is a randomized, double-blind, parallel group, multicenter, Phase 3 transition study in subjects with active RA who are eligible for the subsequent treatment course with US-rituximab or EU-rituximab according to the clinical judgment of the investigator.

It is planned to randomize 140 subjects (70 per treatment arm) at approximately 50 sites in up to 7 countries (including, but not restricted to the United States).

A course of treatment with US-rituximab or EU-rituximab in RA consists of two 1000 mg IV infusions separated by 2 weeks. Subjects with RA who have received at least 1 full course comprising two 1000 mg infusions with either US-rituximab or EU-rituximab will be eligible for the study. The rituximab reference product (US-licensed rituximab [Rituxan] or EU-approved rituximab [Mabthera]) used should be the same in the prior and the randomized treatment course, respectively. Subjects having received the prior treatment course with reference products other than US-licensed rituximab (Rituxan) or EU-approved rituximab (Mabthera) will not be eligible for the study. Subjects should not be switched from the prior to the randomized treatment course from US-licensed to EU-approved reference product or vice versa.

Subjects will then be randomized by interactive web response system (IWRS) to receive either two 1000 mg infusions of DRL_RI (Arm A) or US-rituximab/EU-rituximab (Arm B) on Day 1 and Day 15. This will constitute the next course of rituximab treatment. Subjects randomized to Arm A will receive DRL_RI and subjects randomized to Arm B will continue to receive either US-rituximab or EU-rituximab.

The study will consist of a screening period (Days -14 to 0) and a double-blind period (Day 1 to Week 12). Subjects will attend a screening visit followed by visits at Weeks 0 (Day 1), 2, 4, 8, and 12 (end of study [EOS]) after randomization. An additional follow-up visit will be conducted at Week 26 to evaluate safety and to perform a serum pregnancy test in women of childbearing potential (WOCBP).

[figure not shown]
Subjects having signed the informed consent form (ICF) versions prior to the one introduced by this amendment need to re-consent to continue participating in the study after Week 12 through Week 26. If a subject does not re-consent for further study participation after Week 12, then his/her study data up to Week 12 will be collected and the subject will be discontinued from the study.

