6.2.2 Immunogenicity Assay

Immunogenicity samples will be analyzed by designated analytical laboratory(ies) using validated methods. Analysis of ADA samples will follow a tiered approach of screening, confirmation, and titer determination. Samples that are confirmed positive for ADA will be further tested for titer and NAb using validated assays.

Immunological testing in human subjects will involve a multi-tiered approach as outlined below:

Tier I Screening Assay: All the clinical samples for immunogenicity assessment will be subjected to a screening assay. The methodology is based on the principle of capture of the ADA by the drug and detection by biotin-labelled drug, using ELISA. The test methodology may be modified after the method validation is completed. During method validation, an assay cut point is statistically determined. The samples that show a response equal to or above the pre-determined screening cut point will be called as “screening positive” and the ones that show a response below the assay cut point will be called as “negative”.

Tier II Confirmation Assay: All the clinical samples that are “screening positive” will be subjected to a confirmation assay. This will involve the inhibition of the response seen in the screening assay with high concentration of drug. The assay format is an adaptation of the screening assay, where the samples are spiked with phosphate-buffered saline or drug and incubated for 1 hour at 37°C prior to evaluation according to the screening assay procedure. The samples that show a response equal to or above the pre-determined confirmatory cut point will be called as “confirmed positive” and the ones that show a response below the assay cut point will be called as “negative”.

[figure not shown]
Tier III Titer Determination: It is the semi-quantitative assay where titers of the confirmed ADA-positive samples will be evaluated with respect to a previously established titer cut point. During the clinical sample analysis, serial 2-fold dilutions of confirmed positive samples will be performed and the reciprocal of the dilution able to yield a response at or above the titration cut point will be reported as the titer of the ADAs.

Tier IV Neutralizing Antibodies Assay: This is based on the principle that any sample containing NAbs would reduce or abolish the biological activity associated with a known concentration of drug product used in a cell-based NAb assay. This is based on the mechanism

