of action of the drug (rituximab) and is used to characterize the neutralizing activity of the confirmed ADA-positive samples. Rituximab induces CDC. The ability of the ADA to neutralize the CDC activity of rituximab will be assessed in a cell-based assay. This assay is developed and will be validated prior to clinical sample analysis. This assay is a characterization of the confirmed ADAs.

The diagrammatic representation of the immunogenicity assessment of rituximab in the clinical study is shown in [Figure 6-1](#).

Figure 6-1: Flow Diagram for the Evaluation and Characterization of Anti-Drug Antibodies

Abbreviation: ADA, anti-drug antibody.

Comprehensive information regarding validity, specificity, and sensitivity of immunogenicity assays used in this study will be provided in a separate report.

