8.1. Analysis of Immunogenicity Endpoints

Blood samples for detection of ADA (including NAb) will be collected prior to initiation of the infusion (preferably within 30 minutes before initiation of the infusion) of study treatment on Day 1 and Day 15 and then on visits at Weeks 4, 8, and 12 (EOS/ET).

Summary statistics (frequency and percentage) by treatment arm and overall will be provided for the percent of subject with ADA formation at Day 1 and Day 15, and at weeks 4, 8, 12 (EOS/ET) visit. A subject is considered as ADA positive during the study if the subjects had at least one ADA positive sample otherwise the subject is regarded as ADA negative. Note this will also include any unscheduled visits during the study period.

Additionally, for subjects who are ADA positive at baseline, a shift table per treatment arm will be generated. The shift table includes numbers in each class (decreased, stable, and increased) as well as percentages relative to the number of ADA positive subjects with an available evaluation at the specific visit.

Subjects will be classified at each visit post baseline as:

- Decreased: If ADA titer at post-baseline visit decreases to a lower titer than that observed at baseline. Subjects with positive ADA at baseline in whom a titer is not detectable or non-evaluable at a corresponding post-baseline visit is decreased if the ADA turn negative.
- Stable: If ADA titer equal to that at baseline.
- Increased: If ADA titer increasing to a higher titer than that observed at baseline. Subjects with Negative ADA at baseline in whom a titer is not detectable or non-evaluable at a corresponding post-baseline visit is increased if the ADA turn positive.

The titer and the concentration of confirmed positive results will be reported. In addition, confirmed positive ADA samples will be analyzed for their neutralization potential in a neutralizing antibody (NAb) assay.

The incidence of ADA positive subjects and subjects with NAb will be summarized by treatment arms, by visit and overall. Antibody titers will be summarized by median and quartiles by treatment arm and visit.

A listing of immunogenicity data (including titer, concentration, ADA and Nab status) will be provided.

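### The ADA titer shift table has no tolerance for one 2-fold dilution step, so its Increased and Decreased counts mix assay repeat variation with real titer change

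*SAP*

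**What the plan says.** Protocol 6.2.2 (Tier III) describes titer determination in these terms: "It is the semi-quantitative assay where titers of the confirmed ADA-positive samples will be evaluated". On method it says that "serial 2-fold dilutions of confirmed positive samples will be performed". Adjacent reportable titers therefore differ by a factor of 2.

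SAP 8.1 sets up the shift analysis: "for subjects who are ADA positive at baseline, a shift table per treatment arm will be generated". The three classes, applied at each post-baseline visit, are:

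- "Decreased: If ADA titer at post-baseline visit decreases to a lower titer than that observed at baseline"
- "Stable: If ADA titer equal to that at baseline"
- "Increased: If ADA titer increasing to a higher titer than that observed at baseline"

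A baseline-positive subject who turns ADA negative also counts as Decreased. Neither document gives a minimum fold change, a one-dilution tolerance or a minimum significant ratio. Neither asks for a subject's baseline and later samples to be titrated in the same run. On assay performance the protocol says: "Comprehensive information regarding validity, specificity, and sensitivity of immunogenicity assays used in this study will be provided in a separate report".

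The results go into Tables 14.2.2.3 and 14.2.2.3A (SAP 12.2). SAP 8.1 also plans titer medians and quartiles by arm and visit, and a subject listing that includes titer.

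**The concern.** On a 2-fold dilution scale a true titer lies somewhere between two reportable values. If it lies near a boundary, a small run-to-run error moves the reported titer by a full step. A rule that demands equality then records that step as a rise or a fall although nothing has changed in the subject.

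This matters because many subjects in a transition study may carry ADA from earlier rituximab courses. For them, ADA incidence cannot show boosting after the switch; only a change in titer can. The shift tables are the planned summary of that change within subjects. If a sizeable share of Increased entries is repeat variation, the counts in either arm cannot be read as the number of subjects boosted.

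**Working it through.** The plan states no figure to reproduce, because the point concerns a classification rule. The check asks how often a subject with no true change is called changed.

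**Inputs from the documents.** 2-fold dilutions and a semi-quantitative assay (Protocol 6.2.2); the three class rules (SAP 8.1); classification at Day 15 and Weeks 4, 8 and 12; 70 subjects planned per arm (Protocol 3.1.1).

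**Assumption.** The repeat SD of the titer, s, in log2 steps, is not in the documents. I use 0.1 to 1.0.

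**Model.** Reported log2 titer = floor(T + e), with T uniform within a dilution step and e normal with SD s, independent between samples. Let D be the difference between the two errors, so that D is normal with mean 0 and SD τ = s√2. Then P(reported titers equal) = E[max(1 − |D|, 0)]. Define

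G(c) = E[max(|D| − c, 0)] = 2[τ·φ(c/τ) − c·(1 − Φ(c/τ))].

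It follows that:

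- P(called changed, SAP rule) = G(0) − G(1), with G(0) = τ√(2/π)
- P(called changed, two steps required) = G(1) − G(2)
- P(called Increased) is half of each, by symmetry

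Example, s = 0.5: τ = 0.707, G(0) = 0.564, G(1) = 0.050, G(2) = 0.001. SAP rule: 0.564 − 0.050 = 0.514. Two-step rule: 0.050 − 0.001 = 0.049.

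| s (log2 steps) | Changed, SAP rule | of which Increased | Changed, two-step rule |
|---|---|---|---|
| 0.1 | 11% | 6% | <0.1% |
| 0.3 | 34% | 17% | 0.3% |
| 0.5 | 51% | 26% | 5% |
| 1.0 | 73% | 36% | 30% |

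**Scale.** The baseline ADA prevalence is not stated. For illustration only, Protocol 1.1.1.5 cites 11% positive on at least one visit in pooled rituximab trials. At 11%, 70 × 0.11 = 7.7, or about 8 subjects per arm in the table. With s = 0.25 (28% called changed) to 0.5 (51%), about 8 × 0.28 = 2.2 to 8 × 0.51 = 4.1 of them would be called changed per visit with no true change.

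**When some subjects truly boost.** With a true rise of d steps, D has mean d. The excess probability of being called Increased, boosted minus unchanged subjects, at s = 0.3 / 0.5 / 1.0 is:

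| True rise | SAP rule | Two-step rule |
|---|---|---|
| 2-fold (d = 1) | 0.66 / 0.49 / 0.27 | 0.17 / 0.23 / 0.22 |
| 4-fold (d = 2) | 0.83 / 0.72 / 0.49 | 0.83 / 0.72 / 0.49 |
| 8-fold (d = 3) | 0.83 / 0.74 / 0.59 | 1.00 / 0.95 / 0.70 |

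**What mixing does to the counts.** Suppose 40% of one arm and 10% of the other truly rise 4-fold, with s = 0.5. The SAP rule shows 0.4 × 0.975 + 0.6 × 0.257 = 54% against 0.1 × 0.975 + 0.9 × 0.257 = 33% Increased. The two-step rule shows 0.4 × 0.743 + 0.6 × 0.025 = 31% against 0.1 × 0.743 + 0.9 × 0.025 = 10%. The absolute gap is the same (about 21 points), but under the SAP rule a third of the second arm appears boosted when one in ten is.

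**Link to a minimum significant ratio.** On the underlying continuous scale, 2^(1.96·√2·s) is 1.2, 1.8, 2.6 and 6.8 for the four values of s. At s = 0.3 the ratio is below 2, yet rounding to dilution steps still produces 34% false changes, so a one-step tolerance is needed even then. At s = 1.0 the ratio exceeds 4, so a 4-fold rule would be too lenient.

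**The case against.** The strongest objection is that this is a choice between two defensible rules. Requiring two steps cuts false calls but hides true 2-fold rises, and the tables above show that it separates boosted from unchanged subjects better only for the larger rise examined (8-fold). It ties at 4-fold and does worse at 2-fold. This stands, and it is why the current panel should stay.

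The precision figure is also assumed. At s = 0.1 the false-change rate is 11%, far below the rates at larger values, and at s = 1.0 even the two-step rule miscalls 30%. This stands for the size of the effect. That one-step differences are always tabulated as change does not depend on s.

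The impact is limited as well. The immunogenicity analysis is descriptive (Protocol 7.4.1 and 7.4.5), no decision hangs on the table, and the laboratories are blinded (Protocol 5.7). With perhaps eight subjects per arm, the titer listing can be read subject by subject. All of this stands.

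A reader might infer more than the documents support:

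- *That the shift table is the only view of boosting.* It is not. Titer medians, quartiles and the listing remain. The medians are not paired within subject, however, and may mix baseline-positive with newly positive subjects.
- *That the rule favours one arm or necessarily shrinks the absolute difference between arms.* The same noise enters both arms, and the 4-fold illustration shows no such shrinkage relative to a two-step rule.
- *That false calls should be accumulated over the four post-baseline visits.* SAP 8.1 classifies and reports by visit, so the per-visit rate is the relevant one.

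**Conclusion.** The point holds as a cheap improvement. With Stable defined as exact equality on a 2-fold scale, SAP 8.1 counts every one-step difference as a change. With no true change, the per-visit chance of a false call is 11% to 73% for an assumed repeat SD of 0.1 to 1.0 steps, of which half (6% to 36%) are called Increased. The figures rest on true titers spread evenly within a step, normal errors independent between samples, and a precision that the documents do not give.

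The consequence is limited to interpretation of Tables 14.2.2.3 and 14.2.2.3A, where repeat variation and true boosting cannot be told apart. The documents do not support reading this as a bias between arms, as an error in ADA or NAb incidence, or as a reason to discard the current rule in favour of a fixed 4-fold cut-off.

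**What to change.** Keep the current panel in Tables 14.2.2.3 and 14.2.2.3A and add a second panel to each, defined in SAP 8.1 as follows:

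- Increased or Decreased: a change from the baseline titer beyond the validated minimum significant ratio or, if none is available, of at least 4-fold (two dilution steps).
- Stable: any change within that limit, and in every case a change within one dilution step.
- A baseline-positive subject who turns ADA negative still counts as Decreased, because a subject at the lowest reportable titer cannot fall two reportable steps.

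State the ratio used and cite the assay validation report as its source. Fix the definition before unblinding.

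The cost is a few lines of SAP text and one extra panel in each of two tables, with no new samples or data. In the new panel, true 2-fold changes fall under Stable; the retained panel still shows them.

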Continuous data will be described using descriptive statistics (i.e. n, mean, standard deviation [SD], median, quartiles, minimum, and maximum). Categorical data will be described using the count and percentage in each category. For the summary statistics of all numerical variables unless otherwise specified, minimum and maximum will be displayed to the same level of precision as reported. Mean and median will be displayed to one level of precision greater than the data collected. Standard deviation will be displayed to two levels of precision greater than the data collected.

When count data are presented, the percentage will be suppressed when the count is zero in order to draw attention to the non-zero counts. A row denoted “Missing” will be included in count tabulations where specified on the shells to account for missing values. The denominator for all percentages will be the number of subjects within the analysis population of interest, unless otherwise specified. Percentages will be presented to one decimal place.

For Time Matched Rituximab Concentrations (TMRC) sample, concentration below the lower limit of quantification (BLLOQ) will be converted to '0' for the purpose of quantitative summaries, but will be presented as recorded, i.e. BLLOQ in listings.

Data will be displayed in all listings sorted by subject number and visit, if applicable. Listings will include all visits including unscheduled visits.

"No data available for this report" will be presented when there are no data available to report.

Unless otherwise specified, baseline will be defined as the last non-missing value collected before the first study drug administration. Study day is defined as:

- Visit/examination date – date of first study drug administration when date is prior to the date of first study drug administration (day 1).
- Visit/examination date – date of first study drug administration + 1 when date is on or after day 1.

For summaries by visit, if multiple records fall on the same visit and timepoint, then the record which is the earliest value will be chosen.

Unscheduled results will not be summarized but will be listed, unless otherwise specified. Post baseline summaries will include all values collected after the date of first study drug administration.

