12.2. Tables and Listings

Tables:

Table No.	Table Title	Analysis Population
14.1.1.1	Summary of Screen Failures	All Subjects
14.1.1.2	Summary of Analysis Sets and Reason for Exclusion	All Randomized Subjects
14.1.1.3	Subject Disposition	All Randomized Subjects
14.1.1.4	Study Deviations	Safety Population
14.1.1.5	COVID-19 or Related Events Study Deviations	Safety Population
14.1.1.6	Missed Visit or Assessment Due to COVID-19 or Related Events	Safety Population
14.1.2.1	Demographics Baseline Characteristics	Safety Population
14.1.3.1	Baseline Disease Characteristics	Safety Population
14.1.4.1	Summary of Viral Serology	Safety Population
14.1.5.1	Summary of Medical and Surgical History	Safety Population
14.1.5.2	Summary of Rheumatic Disease History	Safety Population
14.1.6.1	Summary of Prior Medications	Safety Population
14.1.6.2	Summary of Concomitant Medications	Safety Population
14.1.6.3	Summary of Rescue Medications/Re-dosing Medications	Safety Population
14.1.7.1	Summary of Study Drug Administration	Safety Population
14.2.2.1	Summary of ADA and NaB by Visit and Overall	Immunogenicity Population
14.2.2.1A	Estimand 1: Summary of ADA and NaB by Visit and Overall	Immunogenicity Population
14.2.2.2	Summary of ADA titer by Visit	Immunogenicity Population
14.2.2.2A	Estimand 1: Summary of ADA titer by Visit	Immunogenicity Population
14.2.2.3	Shift from Baseline ADA Positive by Visit ADA Positive at Baseline	Immunogenicity Populations

14.2.2.3A	Estimand 1: Shift from Baseline ADA Positive by Visit ADA Positive at Baseline	Immunogenicity Populations
14.2.2.4	Summary of Time Matched Rituximab Concentration by Visit	TMRC Population
14.3.1.1	Overall Summary of Adverse Events	Safety Population
14.3.1.2.1	Treatment Emergent Adverse Events by System Organ Class and Preferred Term	Safety Population
14.3.1.2.2	Study Drug-Related Treatment Emergent Adverse Events by System Organ Class and Preferred Term	Safety Population
14.3.1.2.3	Treatment Emergent Adverse Events by System Organ Class, Preferred Term and CTCAE Severity	Safety Population
14.3.1.2.4	Serious Treatment-Emergent Adverse Events by System Organ Class and Preferred Term	Safety Population
14.3.1.2.5	Study Drug-Related Serious Treatment-Emergent Adverse Events by System Organ Class and Preferred Term	Safety Population
14.3.1.2.6	Treatment Emergent Adverse Events Leading to Treatment Discontinuation by System Organ Class and Preferred Term	Safety Population

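### No planned table directly reports new ADA positivity after a negative baseline, and SAP 8.1 contradicts itself on who the shift table covers; the by-visit denominator is a smaller point to settle alongside.

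*SAP*

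**What the plan says.** **Overall status.** SAP 8.1 treats a subject as ADA positive during the study if the subject "had at least one ADA positive sample otherwise the subject is regarded as ADA negative". Unscheduled samples count. The pre-dose Day 1 sample is not excluded, and Day 1 is one of the visits at which ADA formation is to be summarized.

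**Shift table.** SAP 8.1 says that "for subjects who are ADA positive at baseline, a shift table per treatment arm will be generated". SAP 12.2 lists it as Table 14.2.2.3, "Shift from Baseline ADA Positive by Visit ADA Positive at Baseline", with an Estimand 1 version, 14.2.2.3A. The definition of the 'Increased' class, however, also takes in "Subjects with Negative ADA at baseline in whom a titer is not detectable or non-evaluable" at a later visit, if they turn ADA positive.

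**Denominators.** SAP section 4 sets the default: "The denominator for all percentages will be the number of subjects within the analysis population of interest, unless otherwise specified". SAP 8.1 departs from it only for the shift table, which uses "percentages relative to the number of ADA positive subjects with an available evaluation at the specific visit". The sentence that plans the main summary, "The incidence of ADA positive subjects and subjects with NAb will be summarized by treatment arms, by visit and overall", names no denominator. A row for missing values "will be included in count tabulations where specified on the shells to account for missing values". The shells are not in the documents.

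**Population and endpoint.** The immunogenicity population (SAP 4.3.2) needs only one post-dose ADA result at any time. Inclusion Criterion 3 (Protocol 4.1.1) requires at least one earlier full course of rituximab. The study's immunogenicity endpoint is the incidence of ADA, including titer and NAb (Protocol section 2, SAP 3.2). 'Development of ADA' is the endpoint of Estimand 1, which the SAP labels exploratory.

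**The concern.** Protocol 1.1.3 gives the purpose as ruling out changes in safety and immunogenicity upon a single transition. In a population already exposed to rituximab, some subjects may carry antibodies before the first study infusion. An ever-positive rate that includes Day 1 mixes those carried-over positives with antibodies that appear after randomized treatment. Only the second group speaks to the transition, and two arms can agree on the mixed rate while differing on it.

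The planned tables do not separate the two groups. They are ADA and NAb by visit and overall, titer by visit, the shift table for baseline positives, and Estimand 1 versions of all three. The one place where the SAP describes a change from negative to positive sits inside a table whose text and title exclude the subjects concerned. A programmer could follow the title and drop them. Following the class definition instead would mix new positivity with titer rises.

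The denominator raises a lesser question. A subject with no usable result at a visit cannot enter the numerator but, by default, stays in the denominator. The by-visit rate is then diluted, and unequally so if the arms lose different numbers of samples. Because the analysis is descriptive, these percentages are the result, so the rule should be explicit.

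**Working it through.** The plan states no figure to reproduce: the sample-size sections are redacted and no missing-sample rate is given. Only the 70 per arm (Protocol 3.1.1) comes from the documents. The ADA counts and missing shares below are assumptions for illustration.

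**1. Same overall rate, different new positivity.** Let B be the number positive at Day 1 and T the number newly positive, with n = 70 and complete Day 1 results.

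| | Arm 1 | Arm 2 |
|---|---|---|
| B | 4 | 1 |
| T | 3 | 6 |
| Overall, (B + T)/n | 7/70 = 10.0% | 7/70 = 10.0% |
| New, T/(n − B) | 3/66 = 4.5% | 6/69 = 8.7% |

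The overall row shows no difference, while new positivity differs by 8.7 − 4.5 = 4.2 points. The 95% Newcombe interval for that difference is about −5 to +14 points (Fisher p about 0.49). The example shows what the table can hide; it is not an effect the trial could establish.

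**2. Can it be recovered by subtraction?** If the overall row means ever positive across visits (it could also mean both arms pooled; the SAP does not say), overall minus Day 1 positives gives 7 − 4 = 3 and 7 − 1 = 6. That is correct when Day 1 is complete. Suppose one of arm 1's three has no Day 1 result. Subtraction still gives 3/66 = 4.5%, but documented new positivity is 2/(70 − 4 − 1) = 2/65 = 3.1%. Subtraction cannot tell a negative baseline from a missing one, and the planned summaries do not require the baseline-negative denominator to be shown.

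**3. By-visit denominator.** With rate p among evaluable subjects and missing share m, the full-population percentage is p × (1 − m). For p = 10%:

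- m = 5%: 10% × 0.95 = 9.5%
- m = 10%: 10% × 0.90 = 9.0%
- m = 20%: 10% × 0.80 = 8.0%

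With unequal loss, 6/60 and 5/50 evaluable are both 10.0% but read 6/70 = 8.6% and 5/70 = 7.1%, an artificial gap of 1.4 points.

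**4. Scale.** The 95% Wilson interval for 7/70 is 4.9% to 19.2%. The 95% Newcombe interval for 7/70 against 7/70 is about −10.5 to +10.5 points. The denominator effect is systematic but well inside that.

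**The case against.** The study endpoint is incidence of ADA, and Table 14.2.2.1 reports it. A reader might infer from the words 'Development of ADA' that new positivity is the endpoint and that the plan fails to analyse it. The documents do not support that: the phrase belongs to an exploratory estimand, whose own population-level summary is again incidence. New positivity is a natural reading of the transition question, but the documents do not define it as the endpoint.

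Much of the information is also within reach. Day 1 positivity is tabulated by arm, so a baseline imbalance would show. Subtraction works when Day 1 is complete, and Day 1 sampling is a scheduled step before dosing. Listing 16.2.6.1 holds the subject-level results. The 'Increased' wording may even show an intent to report new positives. All of this stands, and it is why the point says that no table reports new positivity directly. It does not remove the contradiction in SAP 8.1 or supply a prespecified comparison by arm.

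On the denominator, the shells could specify otherwise, and the effect is a point or two. Both objections stand. A row for missing values would not by itself change the stated denominator: SAP 9.3 plans such a row together with the full safety population. Nor is the evaluable rate automatically the true one, since it is unbiased only if missingness is unrelated to ADA status.

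A reader might also infer a large distortion in the Estimand 1 table, where results after death or interfering prohibited therapy are not used. A noticeable effect needs many such subjects in one arm only. For example, 10/70 against 0/70 would be an implausible split under blinded 1:1 randomization (Fisher p about 0.001).

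**Conclusion.** The main point holds on the text alone. Overall ADA status mixes positives present before the first study infusion with those that appear after it, no listed table directly reports the latter among baseline-negative subjects, and the shift-table text conflicts with its own population. How much is hidden depends on how many subjects are positive at Day 1 and how evenly they fall between arms, which the documents do not give. The 4.5% against 8.7% example rests on assumed counts.

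The denominator point is minor. It holds under the written default, subject to the shells, and costs about 0.5 to 2 points for 5% to 20% missing at an evaluable rate of 10%. Neither part shows that the comparison between arms is invalid or that the endpoint goes unreported. This should be corrected before database lock, with moderate confidence about its practical effect.

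**What to change.** In SAP 8.1 and 12.2:

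- **Shift table and new positivity.** Keep Table 14.2.2.3 for baseline positives and remove baseline negatives from its 'Increased' class. Add rows or a table, by arm, for newly ADA-positive and newly NAb-positive subjects, over baseline-negative subjects with at least one post-dose result. Show the number with no baseline result.
- **By-visit rates (Tables 14.2.2.1 and 14.2.2.1A).** For ADA, use subjects with an evaluable result at the visit; in 14.2.2.1A the result must also be usable under Estimand 1. Show by arm the number without one. For NAb, which is tested only in confirmed ADA positives, use the same subjects less confirmed positives with no NAb result, and show that number.
- **Overall rates.** In 14.2.2.1 keep the full immunogenicity population, and show how many overall negatives have missing scheduled post-dose samples. In 14.2.2.1A restrict to subjects with at least one post-dose result usable under Estimand 1, and show how many were cut off early.

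The cost is SAP wording and longer tables, with no new samples and no protocol amendment. Evaluable-sample rates assume that missing samples resemble observed ones, so the missing counts must stand beside them.
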